9. RESEARCH METHODS

9.1 Study Design

This study is a post-authorization, prospective, uncontrolled, non-interventional, multicenter cohort study. Approximately 80 subjects with congenital hemophilia B will be enrolled. Subjects must be prescribed rFIX (RIXUBIS) by the treating physician before study participation. Data will be collected over a period of 4 years from the time of study enrollment. The treating physician will determine the treatment regimen, as well as the frequency of laboratory, radiological, and clinical assessment according to her/his routine. Data will be collected on routinely scheduled and emergency visits. There is no binding visit schedule, however it is recommended that the subjects have at least annual visits. Available data from these visits shall be transcribed onto the electronic case report forms (e-CRFs).

It is considered standard practice for subjects with hemophilia to maintain a diary either on paper or in an electronic form (e.g. Smart Medication) which captures FIX treatment and disease related data. A subject diary will be provided to each subject to assist with the standardization of data collection as stated in Section 9.4.2. Nevertheless, the completion of the diary is a voluntary effort by the individual subject or subject's legally authorized representative. All bleeding events and their treatment recorded in subject diaries during study participation period will be transcribed onto e-CRFs.

QoL questionnaires will be provided at baseline and on an annual basis to subjects or their legally authorized representatives.

As no hypothesis testing or interval estimation will be applied, the sample size for the study is not based on statistical considerations.

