 - FIX regimen used at the time of inhibitor detection
 - Maximum historical titer
 - Local laboratory cut off value for positive inhibitor titer
 - History of ITI therapy, if any, including FIX product and regimen used.
 - Date(s) of inhibitor disappearance
 - Most recent FIX inhibitor test results.
- Current RIXUBIS treatment
 - Dosage and dosing intervals
 - Regimen start date

- Total EDs to RIXUBIS at screening visit
Where exact numbers of EDs is not available, one of the following ranges should be selected: 0, 1-4, 5-20, 21-50, 51-100, 101-150 or >150.
- FIX product used prior to RIXUBIS treatment initiation (maximal retrospective time-period of 12 months before treatment initiation)
 - Name of product, dosage and dosing interval
 - Regimen start and end date
 - Total EDs to FIX products at screening visit
Where exact numbers of EDs is not available, one of the following ranges should be selected: 0, 1-4, 5-20, 21-50, 51-100, 101-150 or >150.
- Sporting activities (type and frequency)
- Ambulatory status, including need for ambulatory assistance devices such as leg braces, cane, crutches, or wheelchair
- Number of bleeding episodes (ABR and annualized joint bleeding rate (ABJR)) categorized by severity within the last 12 months.
- Status of joint health as assessed by physical exam at study enrollment
+ Musculoskeletal evaluation of target joints using HJHS within the last 5 years prior to study enrollment.
- Status of joint health assessed by imaging techniques (e.g. MRI or X-ray)
+radiological evaluation of any joints using the Petterson score within the last 5 years prior to study enrollment.

The following data, if available will be collected at interval and termination visits:

- Total EDs to RIXUBIS since the last visit
- Current RIXUBIS treatment regime (if changed):
 - Dosage and dosing intervals
 - Regimen change date
- Height, Body weight
- FIX inhibitor titer
- Bleed occurrence, including location, etiology, and severity

- Status of joint health as assessed by physical exam
+ Musculoskeletal evaluation of target joints using the HJHS.
- Status of joint health as assessed by imaging techniques (e.g. MRI, X-ray)
+ Radiological evaluation of any joints using the Pettersson score.
- HRQOL measures, surgical data and activity levels (including sporting activities)

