9.7.3.4.3 Joint Health/Function Outcomes

The methods of analysis for the secondary effectiveness endpoints ([APPENDIX 2](#)) are, if available:

- Physical exam using only the pain, bleeding, and physical exam parameters of the Hemophilia Joint Health Score (HJHS) score will be summarized for timepoints 0 (baseline), 12, 24, 36 and 48 months (termination visit) after study start (if available). Linear interpolation (for any time interval) and line extrapolation (for up to 0.5 years) will be used to derive an estimate of the score at these timepoints.
- MRI scoring will be summarized for timepoints 0, 12, 24, 36 and 48 months (termination visit) after study start (if available). Linear interpolation (for any time interval) and line extrapolation (for up to 0.5 years) will be used to derive an estimate of the score at these timepoints.
- Radiographs using the Pettersson score will be summarized for timepoints 0, 12, 24, 36 and 48 months (termination visit) after study start (if available). Linear interpolation (for any time interval) and line extrapolation (for up to 0.5 years) will be used to derive an estimate of the score at these timepoints.
- Number of invasive surgical procedures, such as (not exclusively orthopedic) surgery, radiosynovectomy, and chemosynovectomy per year per subject.

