The Hemophilia Joint Health Score (HJHS)¹⁷ was developed by the International Prophylaxis Study Group (IPSG) as a new scoring system for musculoskeletal evaluation optimized for use in children with no or minimal joint disease. The HJHS is better suited for children aged 4–18 years and all patients on primary prophylaxis than the Gilbert score, which was found to be too insensitive to identify earliest signs of joint disease. The HJHS includes the following parameters: swelling, duration of swelling, muscle atrophy, joint pain, crepitus on motion, flexion loss, extension loss, strength and global gait. The HJHS measures joint health, in the domain of body structure and function (i.e. impairment), of the joints most commonly affected by bleeding in hemophilia: the knees, ankles, and elbows. It can be used when there is a need for orthopedic intervention, or as an outcome measure of physiotherapy interventions. It is appropriate for monitoring joint change over time or assessing effectiveness of treatment regimens in children receiving both prophylactic and on-demand therapy. The HJHS 2.1 provides a total score (higher score is worse; max=124), joint specific scores, and a global gait score. See [Table 5](#). The HJHS total score, calculated from the Sum of Joint Totals and Global Gait Score will be collected during screening, annual, and termination visits or whenever the treating physician deems it appropriate.

Table 5 Hemophilia Joint Health Score (HJHS) for assessing Joint Impairment	
Swelling	0 = no swelling 1 = mild 2 = moderate 3 = severe
Duration (swelling)	0 = no swelling or < 6 months 1 = ≥6 months
Muscle Atrophy	0 = none 1 = mild 2 = severe
Joint Pain	0 = no pain through active range of motion 1 = no pain through active range, only pain on gentle overpressure or palpation 2 = pain through active range
Crepitus on Motion	0 = none 1 = mild 2 = severe
Flexion Loss	0 = < 5° 1 = 5° - 10° 2 = 11° - 20° 3 = > 20°
Extension Loss (from hyperextension)	0 = < 5° 1 = 5° - 10° 2 = 11° - 20° 3 = > 20°

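### The derivation rule for HJHS, MRI and Pettersson scores lets a subject's month-0 value be computed partly or wholly from post-enrolment scores where observed scores are sparse

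*Protocol*

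**What the plan says.** Section 9.7.3.4.3 of the protocol has HJHS "summarized for timepoints 0 (baseline), 12, 24, 36 and 48 months (termination visit) after study start (if available", and lists the same five times for MRI and Pettersson scores. For each of the three it adds: "Linear interpolation (for any time interval) and line extrapolation (for up to 0.5 years) will be used to derive an estimate of the score". It does not exempt month 0, cap the gap between two scores, or ask for an observed score near any timepoint.

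Two other parts of the protocol decide how often the rule will be needed.

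- **Timing of assessments.** Section 9.1 states: "There is no binding visit schedule, however it is recommended that the subjects have at least annual visits". The treating physician sets the regimen "as well as the frequency of laboratory, radiological, and clinical assessment according to her/his routine". Follow-up is fixed only in length: "Data will be collected over a period of 4 years from the time of study enrollment". Appendix 2 says the HJHS total score "will be collected during screening, annual, and termination visits or whenever the treating physician deems it appropriate". It plans Pettersson and MRI scores at screening, interval and termination visits, subject to availability.
- **Historical scores.** The screening list in Section 9.2.6 includes "Musculoskeletal evaluation of target joints using HJHS within the last 5 years prior to study enrollment" and "radiological evaluation of any joints using the Petterson score within the last 5 years prior to study enrollment". It attaches no 5-year look-back to MRI scores.

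**The concern.** A baseline should describe the subject at enrolment and should not depend on what happens afterwards. This rule allows the opposite. If no score was taken at enrolment, a line between an earlier and a later score supplies month 0, and the later score carries part of the weight. If there is no earlier score, a line through two on-study scores may be run back by up to half a year, and month 0 then consists only of later data.

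The means, medians and SDs by timepoint are how the reader will see the course of joint scores over four years, and describing joint health is a stated secondary objective. The fewer scores a subject has, the more of that subject's course is a straight line produced by the method. Change that took place before enrolment can be spread into the study period, and change on study can be spread back before it.

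**Working it through.** The protocol states no figure on this point, so there is none to reproduce. The check applies the rule as written to two scores.

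**Inputs from the protocol:** timepoints 0, 12, 24, 36 and 48 months; unlimited interpolation gap; extrapolation up to 6 months (Section 9.7.3.4.3); look-back of up to 60 months for HJHS and Pettersson (Section 9.2.6).

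**Assumptions:** month 0 is the subject's enrolment. Line extrapolation means extending the straight line through two scores, in either direction. Measurement errors are independent with common variance s². The assessment times are scenarios, because the protocol fixes none.

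**Formula.** For scores S1 at t1 and S2 at t2 (months from enrolment), the derived score at t is

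S(t) = S1·(t2 − t)/(t2 − t1) + S2·(t − t1)/(t2 − t1), allowed for t1 − 6 ≤ t ≤ t2 + 6.

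Its error variance is s² times the sum of the squared weights.

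**Month 0 by interpolation across enrolment.** The weight on the later score is −t1/(t2 − t1).

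| Scores at (months) | Weight of post-enrolment score in month 0 |
|---|---|
| −12 and +12 | 12/24 = 50% |
| −24 and +12 | 24/36 = 66.7% |
| −60 and +12 | 60/72 = 83.3% |
| −60 and +42 | 60/102 = 58.8% |

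**Month 0 by back-extrapolation, no earlier score.**

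- Scores at +6 and +18: S(0) = 1.5·S6 − 0.5·S18. Variance = (2.25 + 0.25)s² = 2.5 s².
- Scores at +6 and +9: S(0) = 3·S6 − 2·S9. Variance = (9 + 4)s² = 13 s².

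Both baselines contain post-enrolment data only.

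**Filling the whole table from two scores.** Scores at −60 and +42 give a permitted value at all five timepoints, the last by 6 months of extrapolation. The derived change from month 0 to month 48 is 48/102 = 47.1% of the difference between the two scores. It is the same 47.1% whether that difference arose entirely before enrolment or entirely after it. Scores at +6 and +42 also fill all five timepoints.

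**Illustration with assumed values.** HJHS is 10 at −60 months and 28 at +48. With t in years from enrolment, S(t) = 10 + 18·(t + 5)/9, which gives 20, 22, 24, 26, 28 at t = 0, 1, 2, 3, 4. The series shows a rise of 8. If the subject was already at 28 at enrolment, the on-study change was 0. If still at 10, it was 18.

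**Out-of-range values.** Extrapolation can leave the scale: scores of 4 at month 36 and 1 at month 42 give 1 − (3/6)·6 = −2 at month 48, below the floor of 0. Interpolation cannot do this.

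**Counter-case.** With observed scores at 0 and 48, the rule returns both, so the overall change is real. Only months 12, 24 and 36 are imputed, with variances (0.75² + 0.25²)s² = 0.625 s², (0.5² + 0.5²)s² = 0.50 s² and 0.625 s². If every timepoint is observed, the rule alters nothing.

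**The case against.** The strongest reply is that the protocol intends the scores that would make the rule harmless. Table 1 marks joint evaluation at screening, interim, annual and termination visits, and Appendix 2 plans HJHS at screening, annual and termination visits. If this happens, months 0 and 48 are observed. That stands, and it limits the point to subjects for whom it does not happen. Such gaps are plausible with no binding schedule and with imaging taken only where available, but the document gives no frequency.

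Further parts of the reply also stand:

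- Section 9.7.3.4.3 names no change from baseline for joint scores, whereas Sections 9.7.3.4.4 and 9.7.3.4.5 do so for quality of life and resource use. The effect is on the timepoint summaries and on any change read from them.
- Section 9.2.6 collects the historical scores as screening data. Nothing says they will anchor a line. Nothing excludes it either, so this is a permitted use and not a stated one. The 5-year wording covers HJHS and Pettersson only.
- The scenarios are chosen to show what the rule permits. The 2.5 and 13 factors apply at the full 6-month limit, and interpolation between close scores is benign.
- Handling after surgery and separate counts of observed and derived values are normally left to the SAP, which is not at hand. They appear below as part of the remedy and are not charged as omissions.

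None of this answers the central point. The rule is fixed in the protocol, it includes month 0, and it has no gap limit.

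**Conclusion.** The point holds conditionally. Followed as written, the rule lets a baseline be partly post-enrolment (50% with scores at −12 and +12 months; 83.3% at −60 and +12) or wholly so (scores at +6 and +18 months, variance 2.5 s²). All five timepoints can be filled from two readings. This assumes sparse scores for the subject concerned and, for pre-study change to appear as on-study change, that historical scores are used as anchors.

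A reader might infer two stronger conclusions. One is that the four-year change in joint scores is an artefact for the study as a whole. The document does not support this, because scores at screening and termination are planned and, where obtained, the overall change is observed. The other is that the joint-health objective cannot be answered. That goes too far as well: the objective is descriptive and also rests on target-joint counts, new target joints and invasive procedures, none of which is interpolated.

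The endpoint is secondary and descriptive, and Section 9.5 does not base the study size on statistical considerations, so there is no power consequence. The rule is still worth correcting, because in a descriptive study the summaries are the result.

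**What to change.** Amend Section 9.7.3.4.3 as follows:

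1. Define baseline as the last observed score at enrolment or within a stated window before it, using no post-enrolment data.
2. Make summaries of observed scores in stated visit windows, with the number observed, the main presentation for all three scores.
3. Remove line extrapolation.
4. If interpolation is kept, use it as a supplementary presentation, only between on-study scores no further apart than a stated maximum gap. Do not run it across a surgery or synovectomy of the joint. Report the observed and derived counts at each timepoint.

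The lengths of the windows and of the gap are for the sponsor to choose and justify. Short-gap interpolation to align unscheduled visits need not be given up.

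The cost is a wording change in the protocol and matching text in the SAP, with no new data collection and no change in study size. The downside is a smaller N at some timepoints, probably most visible for imaging.

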9.3.2.3 Joint Health/Function Outcomes

(see [APPENDIX 2](#))

The health status of the joints (e.g. knee, ankles, elbows) will be further assessed by the following endpoints, where available

- HJHS ¹⁷
- Radiographs, using the Pettersson scale ¹⁸
- Magnetic resonance imaging scoring system
- Total number of target joints ¹⁹
- Number of invasive surgical procedures, such as (not exclusively orthopedic) surgery, radiosynovectomy, and chemosynovectomy per year per patient
- Incidence of new target joints

A target joint is defined as a joint in which at least 3 or more spontaneous bleeds into a single joint within a consecutive 6 month period. Where there have been ≤ 2 bleeds into the joint within a consecutive 12 month period the joint is no longer considered a target joint ¹⁹.

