9.3.2.4.4 Haemophilia-related comorbidities

The following will be recorded:

- Incidence of target joint intervention, including surgery, radiosynvectomy and chemosynvectomy.
- Incidence of pseudotumor development.

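### Joint scores are interpolated and extrapolated straight through surgery or synovectomy on the scored joint, so a local step change appears as gradual change on RIXUBIS

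*Protocol*

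**What the plan says.** Section 9.7.3.4.3 introduces the joint analyses as "The methods of analysis for the secondary effectiveness endpoints". HJHS, MRI and Pettersson scores are each summarised at 0, 12, 24, 36 and 48 months where available. For the radiographs: "Radiographs using the Pettersson score will be summarized for timepoints 0, 12, 24, 36 and 48 months (termination visit"). Each of the three bullets carries the same derivation rule: "Linear interpolation (for any time interval) and line extrapolation (for up to 0.5 years) will be used to derive an estimate of the score". The joint analysis set in section 9.7.1 takes every eligible subject with any assessment.

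Procedures on joints are foreseen. The same section reports "Number of invasive surgical procedures, such as (not exclusively orthopedic) surgery, radiosynovectomy, and chemosynovectomy per year per subject", and section 9.3.2.4.4 records "Incidence of target joint intervention, including surgery, radiosynvectomy and chemosynvectomy". Neither item is linked to the scores of the joint concerned.

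Target-joint status ends on a bleed count alone. After two or fewer bleeds "within a consecutive 12 month period the joint is no longer considered a target joint" (sections 9.3.2.3 and 14.3).

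Elsewhere the protocol does allow for such breaks. Section 9.7.1 takes surgery periods out of the bleed rate, and section 9.7.3.4.4 assesses HaemoQoL change only up to a move to another questionnaire version.

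**The concern.** Linear interpolation assumes steady change between two assessments. A procedure on the joint can act directly on what is scored, such as swelling, pain, motion and the joint surfaces, so a step is to be expected at its date. If the score before and the score after are joined by a straight line, every timepoint between them receives part of the step, including timepoints before the procedure took place. The reader then sees gradual change over years on product where there was none. If the score worsens after the procedure, the same rule produces gradual deterioration.

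The gaps can be long. Section 9.1 sets no binding visit schedule and only recommends annual visits, the scores are collected where available, and interpolation has no limit on the interval. In addition, scores observed after a procedure enter the summary with no mark to separate them from joints managed with factor alone.

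**Working it through.** **Inputs.** From the protocol: the timepoints and derivation rule (section 9.7.3.4.3), the item scores in Tables 5 and 6, and the stated HJHS maximum of 124 (Appendix 2). Assumed, because the protocol gives none: individual scores, procedure dates, procedure rates and the size of a fall.

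**1. The plan's own figure.** Table 5 item maxima per joint: 3+1+2+2+2+3+3+4 = 20. Six joints plus gait: 6 × 20 + 4 = 124, as stated. One joint can carry 20/124 = 16% of the total. Table 6 maxima: 1+1+2+2+2+1+2+2 = 13 per joint for Pettersson.

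**2. Interpolation across a procedure.** Take one joint scored 13 at month 0, operated on at month 40 and next scored s at month 42. The rule gives, at month t, 13 − (13 − s) × t/42.

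| s at month 42 | Month 12 | Month 24 | Month 36 |
|---|---|---|---|
| 0 | 9.3 | 5.6 | 1.9 |
| 4 | 10.4 | 7.9 | 5.3 |
| 8 | 11.6 | 10.1 | 8.7 |

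If the joint in fact stayed at 13 until the procedure, the errors for s = 0 are −3.7, −7.4 and −11.1. For s = 8 they are 5 × 12/42, 5 × 24/42 and 5 × 36/42, that is −1.4, −2.9 and −4.3. All three timepoints precede the procedure.

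**3. Extrapolation across a procedure.** Take scores of 13 at month 24 and 0 at month 42, with the procedure between them. A line through the two has slope −13/18 per month. Six months further on, which the 0.5-year limit allows, month 48 is 0 − 6 × 13/18 = −4.3, below the bottom of the scale.

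**4. Pooling of post-procedure scores.** Shift in the mean HJHS = share of subjects with a procedure × fall in points. At 10% and 6 points: −0.6. At 5% and 3 points: −0.15. At 20% and 8 points: −1.6. These are observed scores and not derivation errors; the issue is that they are unmarked.

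**5. Target joints.** The exit rule looks only at bleeds. A joint that stops bleeding after a synovectomy leaves the total number of target joints (section 9.3.2.3) in the same way as one controlled by factor alone, and nothing in the summary tells them apart.

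**The case against.** The strongest reply is that this is a descriptive, uncontrolled study with secondary joint endpoints collected where available. Summarising every score is then a fair picture of routine practice, procedures are reported in the same section, and finer handling belongs in the stand-alone SAP listed in section 14.1, which is not shown. Much of this stands. The all-scores summary is legitimate and should stay. The reply does not cover the derivation rule, because the protocol itself fixes that rule and, followed as written, it yields values that no assessment supports.

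A second reply is that unlimited interpolation can mislead without any procedure, and that a score at each annual visit would confine the spread to the gap around the procedure. Both are true. A procedure is nevertheless a foreseeable break with a known date, and annual scores are not required.

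A reader might go further in four ways that the documents do not support:
- That the protocol attributes procedural benefit to RIXUBIS. The objective is to describe joint health in subjects receiving it, and no causal claim or test is planned on these scores.
- That comparisons of joint scores between regimens are distorted. Section 9.7.3.4.3 plans no such split.
- That the target-joint definition is wrong. It is a cited published definition, and no resolved-target-joint endpoint is planned.
- That scores should be cut off at the first procedure in the main analysis. That would remove the worst joints from the late summaries and create a selection problem of its own. Nor does the protocol define a Pettersson total across joints from which a missing joint would subtract.

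**Conclusion.** The point holds as a fault in a stated rule: interpolation and extrapolation run across procedures on the scored joint, and post-procedure scores are not identified. For a single joint the error can reach most of the Pettersson range (−11.1 of 13 at month 36 in the extreme assumed case, −4.3 in the milder one), and extrapolation can leave the scale. For the cohort the size is unknown, since the protocol gives no procedure rate; the HJHS illustration of −0.15 to −1.6 of 124 points rests wholly on assumed rates and falls. The primary endpoint is untouched. The change is worth making because it is cheap and matches how the protocol already treats surgery in bleed rates and version changes in HaemoQoL.

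**What to change.** In section 9.7.3.4.3:
- State that no HJHS, MRI or Pettersson score is interpolated or extrapolated across the date of an invasive procedure on that joint. For the HJHS total, which pools joints and gait, the break applies at a procedure on any scored joint. Timepoints that can then not be derived are left missing and counted.
- Keep the all-scores summary. Beside it, show scores separately for joints (or subjects, for the HJHS total) with and without a prior procedure on the scored joint.
- In the target-joint summary, keep the cited definition and list separately the joints that lost target status after a procedure.

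The cost is minor. Table 1 has a row for surgical procedures and section 9.3.2.1 asks for their type and severity, but neither names the date or the joint; Appendix 2 says that the HJHS total is collected. The sponsor should confirm that the CRF holds the procedure date, the joint and the HJHS joint totals, and add the fields if it does not. Somewhat fewer derived values will be available.
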